1.2 Investigational Food

The following foods will be used:

- Resistant potato starch (RPS)
- Corn starch (as placebo)

1.3 Preclinical Data

Murine models have shown that the GI microbiota affect allergic sensitization. When mice are raised in a germ-free environment, gut-associated lymphoid tissue are poorly developed and have lower levels of IgA and IL-10 secreting T regulatory cells, important for oral tolerance. In fact, these mice raised in a germ-free environment are unable to be tolerated to oral antigens. However, when certain bacteria or bacterial components are introduced into germ-free mice, these observations are reversed. Introduction of *B. fragilis* or LPS into germ-free mice can redevelop GALT and induce oral tolerance. In addition, introduction of certain butyrate-producing Clostridium species can increase T regulatory cells and protect against peanut allergic sensitization.¹⁰ Finally, transfer of gut microbiota from food allergic mice into germ-free mice increases the germ-free mice's susceptibility to food allergy; while, transfer of stool from healthy infants, but not milk-allergic infants, protects against anaphylactic responses to cow's milk.²²

One study has looked at the effect of high fiber diet on oral tolerance and the development of food allergy in mice. In this study, mice were fed a high fiber diet containing cellulose and guar gum. The diet reshaped the gut microbial ecology and increased the release of SCFAs, including butyrate. This, in turn, enhanced oral tolerance and protected against food allergy.¹⁸

CONFIDENTIAL

1.4 Clinical Data to Date

One recent single center study compared the dynamics of the gut microbiota and SCFA in response to 2-week dietary interventions with three fibers, resistant starch from potato (RPS), resistant starch from maize (RMS), inulin from chicory root with an accessible corn starch (ACS) used as a control. This study found that RPS resulted in the increase in total SCFAs, including butyrate. In addition, RPS caused an increase in relative abundance of bifidobacteria and the butyrate producing *Ruminococcus bromii* and *Clostridium chartatabidum*.²⁹ The benefits of RPS have similarly been shown in several other chronic, non-infectious inflammatory diseases, including obesity, diabetes and inflammatory bowel disease.³⁷⁻³⁹

1.5 Risks/Benefits

Risks Associated with RPS and placebo (corn starch)

RPS is a food product and generally regarded as safe (GRAS) by the following. Under sections 201(S) and 409 of the Federal Food, Drug, and Cosmetic Act, “any substance that is intentionally added to food is a food additive, that is subject to premarket review and approval by FDA, unless the substance is generally recognized, among qualified experts, as having been adequately shown to be safe under the conditions of its intended use, or unless the use of the substance is otherwise excepted from the definition of food additive. Under sections 201(s) and 409 and FDA’s implementing regulations in 21 CFR 170.3 and 21 CFR 170.30, the use of a food substance may be GRAS either through scientific procedures or, for a substance used in food before 1958, through experience based on common use in food. Under 21 CFR 170.30(b), general recognition of safety through scientific procedures requires the same quantity and quality of scientific evidence as is required to obtain approval of the substance as a food additive. General recognition of safety through scientific procedures is based upon the application of generally available and accepted scientific data, information, or methods, which ordinarily are published, as well as the application of scientific principles, and may be corroborated, by the application of unpublished scientific data, information, or methods.” GRAS notice 310 claims exemption from the requirement of premarket approval for potato fiber and was closed on 12-24-2009 with no questions from the FDA. In addition, under 21 CFR 170.30(c) and 170.3(f), general recognition of safety through experience based on common use in foods requires a substantial history of consumption for food use by a significant number of consumers. Potatoes have been commonly consumed throughout history by numerous populations.

In this study, we are enrolling subjects between the ages of 4 and 17, inclusive with peanut allergy and asking them to consume either a RPS or a control starch (corn starch). This consumption of either product may increase the overall caloric intake of subjects which may lead to weight gain. Subjects in the RPS group will be asked to consume 1 tablespoon (12 grams) of a fiber supplement daily which contains 40 calories/tablespoon. Subjects in the control group will be asked to consume 1 tablespoon (8 grams) of ACS daily which contains 30 calories/tablespoon. In addition, an increase in fiber consumption may lead to bloating, gas and/or constipation.

Risks Associated with DBPCFC

In this study DBPCFCs will be conducted in accordance with the recommended PRACTALL guidelines. The screening DBPCFC is utilized as the standard of care to confirm peanut allergy and does not confer higher than minimal risk than a open label food challenge used clinically to confirm peanut allergy prior to POIT. The screening DBPCFC will also establish a threshold for reactivity for comparison with the exit DBPCFC. The exit DBPCFC will be used to establish efficacy of POIT and confirm safety of accidental ingestion of peanut. The exit DBPCFC also does not confer more than minimal risk above a standard of care open label food challenge used during POIT to confirm tolerance of peanut ingestion. DBPCFC are expected to induce allergic reactions. Reactions range from mild (nausea, few hives) to severe (wheezing, diffuse urticaria, rhinitis/conjunctivitis, vomiting/diarrhea, impending doom) to potentially life threatening (low blood pressure, difficulty breathing, neurologic changes). Administered in a controlled setting under the supervision of experienced staff, food challenges are considered safe and are the

CONFIDENTIAL

current gold standard for the diagnosis of peanut allergy. As soon as symptoms consistent with an allergic reaction are witnessed, interventions to stop the reaction are begun (H1 antihistamines and epinephrine).

Risks Associated with POIT

The most common side effect associated with POIT is GI symptoms, including stomach pain and mouth itching. These are expected to occur in nearly 2/3 of individuals. These symptoms tend to be transient in nature and typically occur in the first few days after up-dosing POIT and for the first hour after taking the dose. GI symptoms are mitigated by eating large meal with each dose and staying well hydrated. Symptoms will be controlled with H1-antihistamines as needed. Systemic allergic reactions/anaphylaxis is also a side effect of POIT. This risk is mitigated by restricting physical activity, hot showers, and NSAID use for 3 hours after daily dosing of POIT. Should symptoms occur, they will be treated with epinephrine. All participants will be required to carry an epinephrine autoinjector. POIT may also be associated with eosinophilic esophagitis. The reported incident is <1% and typically resolves with removal of peanut protein exposure.

Risks Associated with Blood Draw

All subjects enrolled in the study will be asked to undergo a blood draw. The risks involved in drawing blood from a vein may include, but are not limited to, momentary discomfort at the site of the blood draw, possible bruising, redness, and swelling round the site, bleeding at the site, feeling of lightheadedness when the blood is drawn, and rarely, an infection at the site of the blood draw. In order to minimize these risks, blood draws will be done under hygienic conditions by experienced personnel.

Potential benefits of Prebiotic Fiber

The potential benefits of consuming a fiber supplement include reducing constipation, maintaining a healthy weight, lower blood sugar and cholesterol levels. The theoretic benefit to consuming a fiber supplement is that it may improve tolerance of oral immunotherapy to peanut and/or improve immunologic markers associated with peanut allergy. No additional benefit is hypothesized from the control fiber.

Benefits of Oral Immunotherapy (OIT)

The benefit of undergoing peanut OIT is that subjects become “bite-safe” in case of an accidental ingestion of peanut protecting them from a severe, systemic allergic reaction.

2 Study Objectives

2.1 Primary Objective

The primary objective of this study is to determine if prebiotic therapy improves outcomes and reduces side effects associated with POIT.

2.2 Secondary Objective(s)

The secondary objectives of this study are:

- To determine if prebiotic therapy influences the gut microbiome/metabolome
- To determine if prebiotic therapy influences immunological markers associated with peanut allergy

3 Study Design

3.1 General Design

This study is a randomized, double-blind, placebo controlled, single center clinical trial. Subjects are anticipated to be in this study for 1 year with extended, active monitoring for an additional 4 years. After enrollment, screening and randomization, patients will be assigned to consume either RPS or placebo for

CONFIDENTIAL

This material is the property of the University of Chicago.
Do not disclose or use except as authorized in writing by the study PI

05.16.2023

30 days. At the end of the 30 days, patients will begin the standard of care treatment for peanut allergy, peanut oral immunotherapy. Initial dose escalation and up-dosing of POIT plus prebiotic will take approximately 180 days to complete. At the end of the maintenance phase, subjects will undergo a DBPCFC to determine efficacy of treatment. Finally, patients will be monitored for approximately 4 year following completion of the active drug dosing (off prebiotic) therapy during the continued immunomodulation/extended maintenance phase of POIT.

Description of DBPCFC

DBPCFC will be conducted in accordance with PRACTALL guidelines and utilize either peanut flour (Anthony's Organic Peanut Flour) or placebo (Oat Flour; Bob's Red Mill) as previously described. Food challenges will be conducted on two separate days no more than 7 days apart and no more than 30 days prior to initial dose escalation day (for the screening food challenge). Prior to the food challenges, patients will be instructed to stop all antihistamines for 5 days prior to each challenge. All subjects will be free from asthma or atopic dermatitis flare. Asthma will be assessed by auscultation for active wheeze prior to start of the challenge and a peak expiratory flow of greater than or equal to 80% of personal best value. Atopic dermatitis flare will be assessed by investigator examination. Subjects will be admitted to the University of Chicago special procedure unit for initial dose escalation where walls are transparent glass for continuous observation by trained nursing staff. The special procedure area is located immediately above a pediatric dedicated emergency department. Subjects will be monitored on a continuous heart rate and oxygen saturation monitor throughout the procedure. Intramuscular epinephrine and oral antihistamines will be in the room with the patient prior to initiation of any doses. The patient's temperature and blood pressure will be checked before each dose. A resuscitation cart will be available within the area. A resuscitation team will be available within the hospital. Peanut flour and placebo will be mixed in either chocolate pudding and peppermint extract or applesauce and cinnamon to mask flavor and nose clips (as tolerated by the child) will be utilized during consumption to mask flavor. A second bite of vehicle will be given that does not contain challenge material followed by a sip of water prior to removal of nose clips (if nose clips can be utilized). Doses will be given every 15-20 minutes at the following doses: 1mg, 3mg, 10mg, 30mg, 100mg, 300mg (exit only), 600mg (exit only), 1000mg (exit only) peanut protein. Peanut protein constitutes half the peanut flour by weight, thus both peanut and oat flour will be administered in the following weights: 2mg, 6mg, 20mg, 60mg, 200mg, 600mg (exit only), 1200mg (exit only), 2000mg (exit only). Subjects will be monitored for at least 2 hours beyond resolution of symptoms but this period may be extended at the discretion of the investigator.

Reactions will be determined in the following way. Symptoms will be considered consistent with a reaction and the food challenge stopped if the subject experiences any moderate or severe symptoms outlined below. The food challenge will be stopped if the subject experiences two of more mild, symptoms. If the subject experiences one mild subjective symptom, the dose will be repeated before escalation.

Mild Symptoms:

Skin: limited (few) or localized hives, mild swelling, mild skin flushing or mild pruritus (only occasional scratching)

Respiratory: rhinorrhea, nasal congestion, occasional cough, throat discomfort

Gastrointestinal: mild nausea abdominal discomfort, a single minor vomiting episode and/or a single episode of diarrhea

Moderate symptoms:

Skin: systemic hives, significant swelling, pruritus causing protracted scratching, more than a few areas of erythema or pronounced erythema

Respiratory: throat tightness without hoarseness, persistent cough, wheezing without dyspnea

GI: persistent moderate abdominal pain/cramping/nausea, more than a single episode of vomiting and/or diarrhea

Severe symptoms:

Skin: severe generalized urticaria/angioedema/erythema

Respiratory: laryngeal edema, throat tightness with hoarseness, wheezing with dyspnea, stridor

CONFIDENTIAL

[figure not shown]
GI: severe abdominal pain/cramping/repetitive vomiting and/or diarrhea
Neurological: change in mental status
Circulatory: clinically significant hypotension

Description of POIT

Anthony's Organic Peanut Flour will be utilized for POIT, and doses will be prepared by the study PI or by trained study staff under direct supervision of the PI. Peanut flour will be mixed into water to form a slurry and delivered via a medication syringe to optimize at home dosing until doses are sufficiently high to be measured with standard kitchen utensils (i.e. 1/8 teaspoon). Throughout the course of POIT, patients will be instructed to eat a large meal before every dose and will also be instructed to abstain for any activity that will increase his/her heartrate for 3 hours following each dose, including physical activity (other than light walking) and hot showers. No sleep will be allowed during this observation period. Patients will be asked to avoid use of nonsteroidal anti-inflammatory medications throughout the course of oral immunotherapy (acetaminophen will be allowed). No updosing will occur in menstruating women during menses. If a patient develops a fever ($T > 100^{\circ}\text{F}$), asthma flare, or gastrointestinal illness during the course of POIT, dosing will be held for up to two days and restarted upon fever resolution at home. If a fever lasts longer than two days, patients will return to clinic to restart. If more than 2 consecutive days of doses (but less than 7 days) are missed at any time during POIT for any reason (including fever), patients will be restarted at 50% of their current dose under supervision of the investigator but allowed to return to current dosing at home at the discretion of the investigator in 2-4 days. If 7 or more consecutive days of doses are missed, POIT will be restarted under supervision of the investigator at less than 50% of the current dose with a modified updosing schedule.

For initial dose escalation, patients will be instructed to eat a large meal prior to arrival in clinic then eat snacks throughout the morning. Patients will be admitted to the University of Chicago special procedure unit for initial dose escalation where walls are transparent glass for continuous observation by trained nursing staff. Patients will be monitored on a continuous heart rate and oxygen saturation monitor throughout the procedure. Intramuscular epinephrine and oral antihistamines will be in the room with the patient prior to initiation of any doses. The patient's temperature and blood pressure will be checked before each dose. A resuscitation cart will be available within the area. Patients will be dosed every 20 to 30 minutes. Doses given on initial dose escalation day are as follows: 0.5mg, 1mg, 1.5mg, 3mg, 6mg of peanut protein. If patients tolerate at least 3mg on initial dose escalation, they will return the following day for their first monitored dose of 3mg. If the patient tolerates, the 3mg they will continue this dose daily for two weeks then return for updosing. The updosing schedule will be as follows: 3mg, 6mg, 12mg, 20mg, 40mg, 80mg, 100mg, 125 mg, 150 mg, 250 mg, 300 mg. If the patient is experiencing gastrointestinal side effects that do not subside prior to updosing in 2 weeks, updosing may be delayed from 1 week to indefinitely until side effects improve and at the discretion of the investigator. If POIT is discontinued for any reason, patients will continue to be observed on study but not undergo the final DBPCFC (unless the patient withdraws from the study). Patients will continue on 300mg dosing until the end of study at which time they may choose to consent to an extended maintenance study or follow up with their allergist for continued standard of care monitoring and dosing.

CONFIDENTIAL

SCHEDULE OF PROCEDURES									
Phase of Study	SCREENING			INITIAL ESCALATION		UPDOSING	MAINTENANCE	EXIT DBPCFC	
Visit Number	V1	V2	V3	V4	V5	V6 - V14	V15	V16	V17
Visit Day/Month	(D-65)	(D-37)	(D-30)	D1	D2	D16 - M8	M11	M14	M14
Time Window		Within 4 weeks of V1	Within 1 Week of V2	30 Days After V3	1 Day After V4	Every 2-4 weeks	3 months post V14	3 months after V15	Within 1 Week of V16
Informed Consent/Assent	X								
Medical/Allergy History	X								
Interval Medical History				X		X	X	X	
Concomitant Medications	X	X	X	X	X	X	X	X	X
Vital Signs	X	X	X	X	X	X	X	X	X
Physical Exam	X	X	X	X	X	X	X	X	X
QoL Assessment	X								
Spirometry	X	X	X	X				X	X
sNO	X								
ACT Score	X								
Skin Prick Test	X			X				X	
Blood Draw	X			X				X	
Stool Sample Collection		X		X		X (monthly)	X	X	
DBPCFC Randomization		X						X	
DBPCFC Administration		X	X					X	X
Study Arm Randomization			X						
Prebiotic Dispensing/Placebo 7.15 grams			X						
Dosing/AE Log Collection				X		X	X		
SOC Consent for POIT				X					
POIT Initial Escalation				X					
OIT Administration					X	X			

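### Home restart of peanut dosing after an illness hold is tied only to fever, so a short hold for an afebrile asthma flare or GI illness has no resolution condition

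*Combined protocol and SAP*

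**What the plan says.** The sick-day rule is in Section 3.1 General Design, under Description of POIT. It starts with a temperature above 100°F and continues: "asthma flare, or gastrointestinal illness during the course of POIT, dosing will be held for up to two days and restarted upon fever resolution", with the restart at home. The sentence after it reads: "If a fever lasts longer than two days, patients will return to clinic to restart".

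A further rule covers missed doses whatever the cause. It applies to more than two but fewer than seven consecutive days of doses that "are missed at any time during POIT for any reason (including fever), patients will be restarted at 50% of their current dose", under investigator supervision. At seven or more days the supervised restart is below 50%, with a modified schedule.

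Other text that bears on dosing in an unwell child:

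- The same part of Section 3.1: "Throughout the course of POIT, patients will be instructed to eat a large meal before every dose".
- Section 3.1, Description of POIT, on GI side effects that persist when an up-dose is due: "updosing may be delayed from 1 week to indefinitely until side effects improve".
- Section 3.1, Description of DBPCFC, before a food challenge: "All subjects will be free from asthma or atopic dermatitis flare". Asthma is checked by auscultation and "a peak expiratory flow of greater than or equal to 80% of personal best value".
- Section 8.4.3: stopping rule 4 applies when a subject comes to meet an exclusion criterion. Section 4.2 lists uncontrolled asthma and current oral steroid use among these. Stopping rule 6 leaves unacceptable risk to the investigator's discretion.

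**The concern.** By making asthma flare and GI illness reasons to hold in their own right, the protocol itself judges that peanut should not be given during them. A hold protects the child only if something defines when it ends. Here the end condition refers to a sign that two of the three illnesses need not produce.

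What is at stake is a home dose, without supervision, while the illness that prompted the hold is still present. Section 1.5 acknowledges systemic reactions and anaphylaxis as risks of POIT. Section 4.2 excludes only severe or uncontrolled asthma, so children with controlled asthma can enroll and flares are foreseeable.

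**Working it through.** No figure in the plan depends on this rule, so there is nothing to recompute. The check is to match each hold trigger to the rule that releases it, follow one case through, and look for the missing condition elsewhere.

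**Step 1. Match triggers to release rules (Section 3.1, Description of POIT).**

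| Reason for hold | Condition for home restart, hold of two days or less | Illness-based return to clinic | More than two consecutive days of doses missed |
|---|---|---|---|
| Fever | Fever resolved | Fever beyond two days | Supervised, reduced dose |
| Asthma flare, no fever | None stated | None stated | Supervised, reduced dose |
| GI illness, no fever | None stated | None stated | Supervised, reduced dose |

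**Step 2. Apply the restart condition to an afebrile child.** Fever resolution is either satisfied from the outset or has no meaning. On neither reading does it require the flare or GI illness to be over.

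**Step 3. Follow the days.** Suppose an afebrile flare starts and doses are withheld on days 1 and 2.

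- On day 3 the hold has reached its stated limit, and two days have been missed.
- The any-reason rule needs more than two missed days, so it does not yet apply.
- The clinic-return sentence needs a fever, so it does not apply either.
- What is left is a home restart. No reduction is stated for a hold this short, so I read it as the unreduced current dose.

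The any-reason rule counts doses missed, not days of illness. It reaches this child only if someone goes on withholding past the written limit.

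**Step 4. Look for the condition elsewhere.**

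- The flare-free check belongs to food challenges.
- The GI delay concerns side effects and up-dosing. It does not govern resuming a held dose after an illness.
- The large-meal instruction prevents dosing in a child too unwell to eat. It does not prevent it in a child who is wheezing mildly, or has mild diarrhea, and can eat.
- Stopping rules 4 and 6 govern discontinuation. Rule 4 catches asthma that has become uncontrolled, but it does not say when a milder flare is over and does not reach a short GI illness.

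None of these supplies the missing condition. The remaining scope is milder, afebrile episodes with a hold of two days or less.

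**The case against.** The strongest reply is that the sentence is elliptical. If fever resolution counted as already met in an afebrile child, the hold could end as soon as it began and two of the three triggers would do nothing. A sensible reader would take the hold to last as long as the illness that caused it. I accept this as the likely intent. It also means that a reader who infers that the protocol instructs or permits dosing through an active flare goes too far: the text is silent on when these holds end. But staff and families work from the written rule, and the clinic-return sentence repeats the same omission.

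A second reply is that the safeguards are substantial. Besides those above, Section 5.4 requires an epinephrine autoinjector throughout and a daily diary of medication taken for POIT side effects. These lower the severity, but none of them is a restart criterion.

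Third, POIT has its own standard-of-care consent (Section 6.3), which is not part of this text and may carry sick-day instructions. That stands. The point concerns the protocol's wording, and nothing can be inferred about what families are told.

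Fourth, a food challenge escalates well beyond a daily dose, to a 1000 mg step at exit, so its flare-free requirement is a weak comparator. It shows that the protocol regards an active flare as relevant to peanut exposure. It does not measure the risk of a home dose.

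**Conclusion.** Wrong as written, minor severity. After a hold of two days or less for an afebrile asthma flare or GI illness, the protocol does not require the illness to have resolved before the current dose resumes at home.

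The conclusion rests on two assumptions: that no stated reduction means the unreduced dose, and that no other document in force supplies the condition. The documents give neither the frequency of such illnesses nor the share of children with asthma, so the size of the problem cannot be expressed as a number of children or events.

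Two stronger readings are tempting and are not supported:

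- A reader might set the maintenance dose ("Patients will continue on 300mg dosing until the end of study") against half of it, 0.5 × 300 = 150 mg, as the size of the hazard. That contrast reflects how many days were missed, not whether the child is ill. Counting how many of the three triggers each sentence names does not measure risk either.
- A reader might infer an effect on the exit food challenge, the side-effect endpoints or the comparison of arms. Nothing in the documents shows one, and none is claimed.

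**What to change.** Amend the two adjacent sentences in Section 3.1, Description of POIT, so that both cover all three illnesses. For example: dosing pauses for no more than two days and resumes at home once the fever, asthma flare or gastrointestinal illness behind the pause has resolved; should any of the three persist beyond two days, the child comes back to clinic to restart.

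The second clause agrees with the existing any-reason rule and removes the case in Step 3 where the hold expires while the illness continues.

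The cost is a few extra missed doses, and some children moved to the supervised half-dose restart who would otherwise have resumed at home. Under the existing rule they may return to their current dose at home in 2 to 4 days at the investigator's discretion. Days missed through illness do not count toward stopping rule 1, which covers non-compliance only. They do count toward stopping rule 2, which is 14 consecutive days for any reason.

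I would not go further. A home peak-flow criterion would need equipment not otherwise required for home dosing, in a trial that enrolls from age 4. A new pointer to stopping rule 4 could prompt discontinuation of POIT over a brief oral steroid course, and with it the loss of the exit food challenge, a cost out of proportion to this gap.

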3.2 Primary Study Endpoints

The primary endpoint is the proportion of subjects who tolerate at least 1043 mg cumulative of peanut protein with no more than mild symptoms at the 12 month DBPCFC

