6.5 Visits 6-14 (every 2-4 weeks)

- Interval medical history
- Vital signs
- Physical examination, including height and weight
- Stool sampling (monthly)
- Collection of logs

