6.6 Visit 15 (3 months after visit 14)

- Interval medical history
- Vital signs
- Physical examination, including height and weight
- Stool sample collection
- Collection of logs

Visit 15 (3 months after visit 14; virtual)

- Interval medical history

CONFIDENTIAL

This material is the property of the University of Chicago.
Do not disclose or use except as authorized in writing by the study PI

05.16.2023

- Height and weight
- Stool sample collection
- Collection of logs

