6.7 Visits 16 and 17 (3 months after visit 15)

- Interval medical history (visit 16 only)
- Vital signs
- Physical examination, including height and weight
- Stool sample collection (visit 16 only)
- Skin prick test (visit 16 only)
- Blood draw (visit 16 only)
- Spirometry (if has asthma diagnosis; as COVID allows)
- DBPCFC

7 Statistical Plan

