8.4.3 Individual Stopping Rules

Individuals may stop participation at any time for any reason, including inability to tolerate study related side effects. If individuals discontinue either study drug treatment or POIT treatment at their discretion or because they meet an individual stopping rule, they will continue to be monitored for the length of

CONFIDENTIAL

This material is the property of the University of Chicago.
Do not disclose or use except as authorized in writing by the study PI

05.16.2023

the study unless the subject withdraws consent. Subjects will not undergo a DBPCFC at exit unless the subject reaches POIT maintenance dosing of 300mg peanut protein for 6 months.

Specific individual stopping rules are as follows:

1. A subject misses 5 or more consecutive days of POIT or study drug dosing due to non-compliance (but not illness)
2. The subject misses 14 consecutive days of POIT or study drug dosing for any reason
3. Administration of three or more doses of epinephrine as a result of an allergic reaction caused by a single POIT dose
4. Meeting any exclusion criteria during the course of the study
5. Development of eosinophilic esophagitis (biopsy proven)
6. Any reason at the discretion of the investigator that continued participation in this study places the subject at unacceptable risk or for any reason prevents safe conduct of the study.

In this study, if a subject fails to tolerate an updose after 3 or more attempts but do not meet the aforementioned stopping criteria, the subject will continue maintenance dosing at the last tolerated dose indefinitely. Failure to tolerate an updose after 3 or more attempts is not an individual stopping rule for purposes of this study.

9 Data Handling and Record Keeping

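### The dose ladder needs ten increases but the schedule lists nine updosing visits, so V16 as timed falls short of the six months at 300 mg required for the exit challenge

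*Combined protocol and SAP*

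**What the plan says.** Under Description of POIT, section 3.1 gives the ladder: "The updosing schedule will be as follows: 3mg, 6mg, 12mg, 20mg, 40mg, 80mg, 100mg, 125 mg, 150 mg, 250 mg, 300 mg". After initial escalation, children who tolerate at least 3 mg go to V5: "they will return the following day for their first monitored dose of 3mg". They stay on that dose for two weeks before the first increase. Section 6.4 likewise lists V5 as the 3 mg start.

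The visits are set by the headings "6.5 Visits 6-14 (every 2-4 weeks", "6.6 Visit 15 (3 months after visit 14" and "6.7 Visits 16 and 17 (3 months after visit 15". The Schedule of Procedures repeats these intervals and prints D16 to M8 for V6–V14, M11 for V15 and M14 for V16 and V17. V15 is labelled maintenance and carries no mark for POIT administration. Section 6.6 lists V15 twice, once as a virtual visit, and neither list contains an updose.

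Under section 8.4.3 there is no exit challenge "unless the subject reaches POIT maintenance dosing of 300mg peanut protein for 6 months". Section 3.2 reads the primary endpoint "at the 12 month DBPCFC", without saying from which day the months run. The Study Summary describes about 180 days of POIT updosing and then 180 days of maintenance before the challenge.

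On screening, section 3.1 places the challenges "no more than 30 days prior to initial dose escalation day (for the screening food challenge", while the schedule has V2 at D-37, V3 at D-30 and V4 30 days after V3.

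**The concern.** The ladder, the visit list and the condition for the exit challenge do not fit together. The visit list ends one step below 300 mg, yet the six months before the exit challenge are counted from the end of that list and not from the first 300 mg dose.

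At stake is who gets the measurement that defines the primary endpoint. The exit challenge is its only source, and section 7.2 does not say how a child without one is counted. With 30 children randomised 1:1, there are 15 per arm and each child is 1/15 = 6.7 percentage points of an arm's proportion. Someone will have to decide whether a little under six months qualifies, and the protocol gives no rule for that decision.

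**Working it through.** **Inputs.** Eleven dose levels (3.1). Start at 3 mg at V5, D2 (3.1, 6.4). First increase at V6, D16 (3.1, schedule). Updosing visits V6 to V14, 2 to 4 weeks apart (6.5, schedule). V15 = V14 + 3 months; V16 = V15 + 3 months (6.6, 6.7, schedule). I take a month as 30.44 days and three months as 91.3 days.

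**Count.** Increases = 11 − 1 = 10. Updosing visits = 14 − 6 + 1 = 9. At one step per visit: V6 = 6, V7 = 12, V8 = 20, V9 = 40, V10 = 80, V11 = 100, V12 = 125, V13 = 150, V14 = 250 mg. No listed updosing visit reaches 300 mg.

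**The plan's own calendar.** With spacing w days, V14 = D(16 + 8w) and V16 = V14 + 2 × 91.3 days. At w = 28, V14 = D240 (M7.9) and V16 = D423 (M13.9). This reproduces the printed M8 and M14, so those months correspond to nine visits at four-week spacing.

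**Time at 300 mg at V16.** Suppose the tenth increase takes place at an unlisted visit one interval after V14, on D(16 + 9w). Time at 300 mg at V16 is then 182.6 − w days.

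| Spacing | V14 | Unlisted tenth visit | V16 | At 300 mg by V16 | Six months after tenth visit |
|---|---|---|---|---|---|
| 14 days | D128 (M4.2) | D142 (M4.7) | D311 (M10.2) | 169 days (5.5 months) | D325 (M10.7) |
| 21 days | D184 (M6.0) | D205 (M6.7) | D367 (M12.0) | 162 days (5.3 months) | D388 (M12.7) |
| 28 days | D240 (M7.9) | D268 (M8.8) | D423 (M13.9) | 155 days (5.1 months) | D451 (M14.8) |

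The shortfall equals one interval, 2 to 4 weeks. It arises at any spacing because V15 and V16 are tied to V14. The second challenge day, V17, is at most 7 days later, which still leaves 7 to 21 days. If 300 mg starts at V15, time at 300 mg at V16 is 3.0 months, 3 months short.

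**Time label.** The last challenge falls between about M10 and M14 from D1 before any delay, against a stated 12 months and a printed M14. The Study Summary's 180 + 180 = 360 days is 11.8 months from the start of POIT.

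**Screening limit (separate).** V3 is 30 days before V4. V2 is on a different day, up to a week before V3, so V2 is 31 to 37 days before V4. The first challenge is therefore 1 to 7 days outside the 30-day limit.

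**The case against.** The strongest reply is that nine is a nominal count. The protocol lets updosing be delayed for gastrointestinal side effects, provides a modified schedule after missed doses, and expects repeated attempts at an updose, so more than nine visits are foreseeable. The calendar months also leave room. Ten increases fit between D16 and M8 at any spacing up to (243.5 − 16)/9 = 25.3 days, and at 14 or 21 days the six months at 300 mg end at M10.7 or M12.7, before the printed M14. On that reading the defect is one visit missing from a label.

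This stands as a limit on the consequence. A reader might infer that no child could qualify for the exit challenge. That needs exactly nine visits, V15 and V16 held strictly to V14, and no tolerance on six months. The documents state the link to V14 and are silent on tolerance, but they do not hold updosing to nine visits. The reply does not remove the contradiction: sections 6.6 and 6.7 count from V14, and section 8.4.3 counts from 300 mg.

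A reader might also infer bias between arms, since side effects slow updosing and may differ by arm. That does not follow from the miscount. Exit timing would depend on updosing speed with ten visits too, and the condition in 8.4.3 makes time on maintenance more uniform.

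The 12-month label is a softer point. Its origin is undefined, three-week spacing gives M12.0, and there is only one exit challenge, so the measurement meant is not in doubt. On screening, counting the 30 days from the second challenge alone would remove the conflict, but section 3.1 does not say that.

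**Conclusion.** The concern holds as an internal contradiction that should be fixed. Ten increases against nine updosing visits is an exact count. Followed literally, V16 comes 2 to 4 weeks before six months at 300 mg if the last step is taken one interval after V14, and 3 months before if it is taken at V15.

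This assumes one ladder step per visit from 3 mg at V5, with no skipped step and no increase at home; the protocol describes neither. It also assumes V15 and V16 are timed from V14 as written. The documents do not support the stronger conclusions that all 30 children would be ineligible or that the miscount biases the comparison of arms. The 12-month label against M14, and the 1 to 7 days by which the first screening challenge exceeds its limit, are minor. The screening point has no demonstrated effect on the primary endpoint.

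**What to change.** Reconcile two pairs of statements: the number of updosing visits with the number of dose steps, and the event from which V15 and V16 are counted with the condition of six months at 300 mg. State whether any tolerance applies to the six months. The affected places are the Study Summary, section 3.1 including the Schedule of Procedures, sections 6.5 to 6.7 and section 8.4.3. Which element changes is for the clinical team.

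In the Study Summary and section 3.2, define the primary endpoint by the exit challenge and its qualifying event. No single month fits a calendar that varies by child. Record each child's days at 300 mg at the exit challenge.

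Separately, reconcile the 30-day screening limit in section 3.1 with V2 at D-37 and V4 30 days after V3.

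The cost is one protocol amendment and one derived data item, with no added subjects.
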